9. METHODOLOGY

9.1 Study Settings

The study will be conducted at research centers of the council in coordination with the homoeopathic medical colleges. The identified scientists and faculty of the college will be involved in the study for enrollment of participation, distribution of study drug, recording & reporting of symptoms of the volunteers.

9.2 Eligibility criteria:

9.2.1 Eligibility for study

Ages:	18-60 years
Genders:	Both male and female
Health status:	Good state of health both somatically & psychologically

9.2.2 Inclusion Criteria:

- Healthy individuals with no apparent disease and normal routine laboratory parameters during screening
- Healthy individuals identified as fit for proving by experts
- Intelligent enough to record carefully the facts, subjective and objective symptoms generated by the IPS during proving.
- Able to be informed of the nature of the study and willing to give written informed consent

9.2.3 Exclusion Criteria:

- Any disease or condition which might compromise the hematopoietic, renal, endocrine, pulmonary, central nervous system, cardiovascular, immunological, dermatological, gastro-intestinal or any other body system
- Persons with colour blindness.
- Persons who have undergone surgery in last two months.

- Planned medical / dental treatment during the proving period including herbal or dietary supplements, procedures, or medications that are likely to interfere with, or substantially alter, responsiveness to the proving substance.
- Volunteers on regular medication (allopathic, ayurvedic, homoeopathic, naturopathic, unani, etc.) for any acute or chronic disease.
- Participant must not be on any homoeopathic remedy in the preceding one month and have had no significant change in health status in last one month.
- Emotionally disturbed, hysterical or anxious persons.
- Persons having known history of allergies, food hypersensitivity, etc.
- Women during pregnancy, puerperium and while breast-feeding and women who have undergone hysterectomy.
- Smokers who smoke more than 10 cigarettes per day
- Recent history of alcoholism / drug addictions or unlikely to refrain from excessive alcohol consumption / drug intake during the study period
- Participation in another clinical or proving trial during the last 6 months

9.3 Sample size:

Each drug will be proved on a minimum of 30 participants, including 30% control. Adding 20% dropout, minimum volunteers needed to enroll in proving becomes 40. Each centre must enroll minimum 15 to a maximum of 25 volunteers in proving. Efforts are to be taken to include atleast 20% volunteers from non-homoeopathic background.

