9.4.8 Blinding

The study will be a double blind study, where the site investigators and the participants at the study site will be kept blind about nature of drug substance and the allocation of participants in the verum and placebo groups. The study medication will be sent in coded forms along with a randomization chart. The nature of the proving substance will be known to the PI and the Co-I/coordinator, but the site investigators and the participants will be blind to the nature of the IPS. The coded study medication will be labeled with the UIC and sent to the proving site.

9. 4.9 Interventions

10.3.1 Arms	Assigned Interventions
Group I : IPS	The verum group will be advised to take the study medication as per schedule. This group will comprise of about 70% of the enrolled participants. The IPS will be given in multiple batches, out of which 1 batch will be placebo and other batches will be IP.
Group II: Placebo	The control group will be given placebo indistinguishable from the study medication. This group will comprise of about 30% of the enrolled participants. Multiple batches will be given, all of which will comprise of placebo.

Both the drug and the placebo will be same in appearance, odor and taste.

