9.4.12 Dosage schedule

Each batch will have 12 doses. The provers will be instructed to take 4 pills, 4 times a day at four hourly interval for 3 days.

In case of drugs which the Council proposes to re-prove considering that the previous proving has generated very few symptoms, the following dosage schedule is proposed:

Day	Number of pills*	Number of doses
1	4	4 times
2	8	4 times
3	12	4 times

* the number of pills taken on each day will be increased consecutively in concordance with the Organon of medicine (Aphorism 129), where in it is mentioned that “a few more globules may be taken”^[6]

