- G.** Symptoms that involve multiple body parts or organs in a similar manner or multiple symptoms within the same subject with a similar associated modality, forming an easily recognizable pattern of reaction
- H.** Similar symptoms occurring in multiple provers. Such symptoms may be related by similar sensation, modality, or body system and can be recognized through a qualitative analysis similar to red – line symptom reporting in homoeopathic literature.
- I.** Any objective finding/including abnormal laboratory values associated with subjective symptoms.

14.1.3 Grading of the Drug Proving Symptoms as per their value:

Symptoms will be graded as follows:

Grade I symptoms:

- Symptoms appearing in more than 2 provers, at two different study sites (Symptom in 1 or more prover at one site and similar symptom in 1 or more provers at the second site. i.e. if two provers separated by distance and time with no contact with each other what so ever give the same symptom).
- Peculiar, rare, queer, strange, characteristic symptoms
- Symptoms reappearing from prior provings.

Grade II symptoms

All proving symptoms other than those in grade I

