24.2 Investigational Proving Substance (IPS)

Drugs with potential to develop pathogenetic effects will be investigational proving substances under the study. Only single drug will be used for proving at a time in a prover.

1. These could be drugs already existing in the Indian/international homoeopathic pharmacopoeias/ formularies.
 - a. These are those drug substances whose basic standardization and safety parameters are known.
 - b. These could include drugs proved and used in homoeopathy or drugs fragmentarily proved, but used in homoeopathy; drugs not proved, but being used in other systems of medicine.

These drugs will be proved in potentized form in different potencies. In case where specific safety data about the drug substance is available for lower dilutions and potencies, the drug can also be used for proving in lower dilutions.

2. New products, with no reported use in homoeopathic system of medicine in any literature will be considered as new drugs. In such a case standardization and safety studies shall be completed before undertaking human proving. The first safe dilution (FSD) would be identified in this case and proving would be conducted only in potencies/dilutions higher than the identified FSD.

In either case, safety and standardization parameters will be recorded and compiled, before initiation of drug proving. The detailed literature review compiling the summary of findings from previous proving & clinical trials known and potential risk and benefits to human subjects will be prepared before initiation of the proving. The drug monograph will reflect the details of the IP including Latin name, chemical name, common names, source, origin, habitat, collection, pharmacognosy, physico-chemical parameters, pharmacological aspects, etc. A certificate of authenticity of this nature will be procured from the manufacturing firm.

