9	Participant is on regular medication (allopathic, ayurvedic, homoeopathic, naturopathic, unani, etc.) for any acute or chronic disease.		
10	Participant is on any homoeopathic remedy in the preceding one month		
11	Participant has had significant change in health status in last one month.		
12	Participant is emotionally disturbed, hysterical or anxious persons.		
13	Persons has a history of allergies, food hypersensitivity, etc.		
14	Participant is a pregnant woman		
15	Participant is a women, presently under peurperium		
16	Participant is a nursing mother		
17	Participant smokes more than 10 cigarettes per day		
18	Participant has a recent history of alcoholism / drug addictions		
19	Participant is unlikely to refrain from excessive alcohol consumption / drug intake during the study period		
20	Person has participated in another clinical or proving trial during the last 6 months		

If YES to 1-4 and 'No' to all other parameters, proceed for detailed history taking and general examination of the participant as per Form D, Part – I.

Name of Investigator _____
 Signature of Investigator _____

Date: ____/____/____
Day/month/year

Form D

CENTRAL COUNCIL FOR RESEARCH IN HOMOEOPATHY
Homoeopathic drug proving: Randomized double blind placebo controlled trial
PRE-TRIAL MEDICAL REPORT PROFORMA
Research Institute/ Unit.....

Date.....

Regn. No.

Proving code (to be provided by CCRH, Hqrs.).....

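### A previous prover of the same substance can enter its re-proving, and Grade I for a symptom that reappears from a prior proving does not require a different person

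*Protocol*

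**What the plan says.** **Eligibility.** Section 9.2.3 lists "Participation in another clinical or proving trial during the last 6 months" as an exclusion. Item 20 of the screening form (Form C) repeats it: "Person has participated in another clinical or proving trial during the last 6 months". The only other criterion that touches earlier exposure looks back one month: "Participant must not be on any homoeopathic remedy in the preceding one month". No criterion or form item asks whether the volunteer has proved this particular substance before.

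**Re-proving.** Section 9.4.12 provides a schedule for "drugs which the Council proposes to re-prove considering that the previous proving has generated very few symptoms". Section 24.2 says of eligible substances: "These could include drugs proved and used in homoeopathy".

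**Grading.** Section 14.1.3 has three routes to Grade I. The third is "Symptoms reappearing from prior provings", with no further condition. The first concerns the same symptom in provers at two different sites, and explains that these provers are to be remote from and unknown to each other.

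**Blinding and enrolment.** Section 9.4.8 states that "the site investigators and the participants will be blind to the nature of the IPS", while the principal investigator and the coordinator know what is being proved. Under section 9.4.5 the pre-trial medical file goes to headquarters before the unique identity code (UIC) is issued. No comparison with earlier provings is prescribed there.

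**The concern.** A symptom that appears again in a second proving deserves a higher grade because the second report is taken as confirmation of the first. That holds only if the two reports are independent. Two reports from one person are not: people tend to get their own symptoms again, whatever they are given.

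As written, the protocol lets the same person supply both reports. The symptom would then enter the drug picture at the highest grade as a replicated finding, although only one person has ever shown it. Section 6.2 gives reproducibility and reliability of symptoms as the reason for standardizing the process, so this works against the protocol's own aim.

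**Working it through.** The protocol gives no figure on this point, so the check follows one returning prover through the rules.

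1. **Can the person be enrolled?** Yes, once six months have passed since the last trial and one month since any homoeopathic remedy (9.2.3; Form C, items 10 and 20). Recruitment under 9.4.1 is by notice board among students, faculty and staff of the participating colleges, and 6.1 describes a continuing programme. Repeat volunteering is therefore possible.

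2. **Would anyone notice?** The site and the volunteer cannot, since both are blind to the substance (9.4.8). Headquarters could: it knows the substance and receives Form D, which carries name and date of birth. No rule tells it to look.

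3. **How is the repeated symptom classified?** Sections 9.4.16, 13.2 and 24.9 leave these options:

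| Status of the symptom in the returning prover | Class | Proving symptom? |
|---|---|---|
| Never experienced before | NS | Not applicable: the person reported it in the earlier proving |
| Habitual, same pattern as usual | U | No, to be left out |
| Ongoing or recurring, unexpectedly worse or better | C- or C+ | Yes |
| Resolved, not expected back, returns | RS | Yes |

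The last two rows pass. The 12-month symptom-free condition in 14.1.2 (feature D) is a characterizing feature. It does not decide whether an RS symptom counts under 13.2.

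4. **Does placebo matching remove it?** Section 13.4 drops symptoms that are identical under drug and placebo in location, sensation, modalities and concomitants. A symptom with no exact placebo match stays, whoever reported it.

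5. **Which grade does it get?** It appeared in a prior proving and appears again, so the third route of 14.1.3 applies as worded.

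The two replication routes in 14.1.3 compare as follows:

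| Route to Grade I | Different persons required? |
|---|---|
| Same symptom at two sites within the proving | Yes, spelled out |
| Reappearance from a prior proving | Not stated |

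Both routes rest on replication, but only one protects its independence.

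**The case against.** The other side has several good arguments.

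- **Regular complaints are already filtered.** A reader might infer that any complaint a person gets every month or two would count as RS and so reach Grade I. The definitions do not support this. Section 24.9 reserves a past symptom for something resolved and not expected back, and treats an expected complaint as an existing symptom. If unchanged, it is not reported (13.2). Form C, the recurring-complaints item in Form D, the run-in diary of at least two weeks (9.4.14) and the Form F instruction to use those records all help to identify such complaints. This stands, and it confines the point to RS, C- and C+ symptoms.
- **Few symptoms to repeat.** The re-proving schedule is for drugs whose previous proving yielded little, and other prior provings may be old or done elsewhere, where shared volunteers are unlikely. This limits the reach of the point but does not remove it.
- **Grade I does not always need a second person.** Peculiar symptoms qualify from one prover, and 14.1.1 counts repeated occurrence as evidence without requiring a second person. That is true, but the peculiar-symptom route makes no claim of replication. The reappearance route does.
- **Nothing is lost.** All symptoms are kept whatever their grade (14.1.1) and serve as baseline data for later verification (6.2). This stands and lowers the stakes.
- **Headquarters may notice a returning prover.** It may, but a possibility is not a rule.

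**Conclusion.** The gap is real but minor. Followed as written, sections 9.2.3, 9.4.12 and 14.1.3 together allow a resolved symptom that returns, or an ongoing symptom that changes, to be graded I as a reappearance from a prior proving on the word of one person.

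This rests on three conditions: the substance has been proved before, the earlier proving drew on the same pool of volunteers, and a prover from it returns.

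No rate can be attached. A reader might try to calculate a chance from an assumed recurrence interval and the length of the observation windows. Such a figure would describe the regularly recurring complaint that the protocol filters as unchanged, and it would need a number of returning provers that the document does not give. It would also need the design of the earlier proving. Nor does the text support a claim that Grade I lists in general are unreliable for this reason. The point concerns one of three routes, in re-provings only.

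**What to change.** 1. **Section 14.1.3, third Grade I route:** add the words *in a different person*, to apply wherever the identity of the provers in the prior proving is known. This closes the same-person path even if a returning prover is enrolled unnoticed.

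2. **Section 9.2.3:** add an exclusion for previous participation in a proving of the same substance. Place the check in 9.4.5, at headquarters, against the Council's own prover records when the UIC is issued. The site should be told only that the volunteer is not enrolled, without the reason, so that it learns nothing about the substance.

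The cost is two lines of text, a look-up in existing records, and the loss of perhaps a few volunteers in re-provings. The look-up cannot reach provings run by others or those whose records are no longer held. In those cases overlap of persons is least likely for provings run elsewhere, and for the rest the check simply cannot be made.

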9.4 Proving Process

9.4.1 Screening of volunteers

Applications (**Form A**) from interested volunteers will be invited which may include students, faculty & staff of homoeopathic medical colleges through notices on notice boards of the Institutes/Units/College. The study investigator(s), college teachers may motivate the students and staff of the Homoeopathic Medical College to participate in the Proving Programme. For non – homoeopathic volunteers, members from general local bodies and attendants of the participants visiting the institute/ unit will be motivated.

9.4.2 Written Voluntary Informed Consent

All volunteers will be informed about the objectives, drug proving process, benefits of the trial and anticipated risks through a Provers Information Sheet (**Form B part 1**). A 'Written Informed Consent' (**Form B part II**) will be obtained from each selected volunteers before starting the drug proving process.

9.4.3 Screening of participants

The volunteers will be subjected to a detailed screening comprising of history and general examination (**Form C**). Volunteers identified as healthy will be enrolled as participants.

9.4.4 Pre-Trial Medical Examination

A detailed pre-trial medical examination (PME) of all participants will be taken up through a detailed history, clinical (general & systemic) examination & laboratory investigations to confirm health status of the participants. Volunteers identified as healthy by experts will be enrolled in proving.

PME will comprise of:

Process	To be done by	Form
History & General Examination	Site Investigator	Form D, Part-I
Chest X ray	Identified Radiology Lab/In house laboratory	Form D Part II

Haematological & Bio-chemical examination	Identified Pathology Lab/ In house lab	Form D Part II
Abdominal ultrasonography	Identified Radiology Lab/In house lab	Form D Part II
Psychological examination	Consultant psychiatrist	Form D, Part III
Respiratory, Gastro-intestinal, cardiology, neurology, examination, genito-urinary	Consultant medicine expert	Form D, Part III
Gynaecological examination (female participants)	Consultant gynaecologist	Form D, Part III
Dermatology examination	Consultant dermatologist	Form D, Part III
Eye examination	Consultant ophthalmologist	Form D, Part III
ENT examination	Consultant ENT consultant	Form D, Part III
ECG	Identified ECG lab/ In house lab	Form D Part III

Photographic record: One photograph of each selected volunteers in full pose, facing camera for record will be included in the PME. This will be only for record purposes, to assess constitution/physical makeup. Photos will not be disclosed in the research data and or compiled data or in the publication.

Duration: The total PME examination of a volunteer must be completed within two weeks.

9.4.5 Enrollment of provers

The PME of the participants found fit as identified by the site investigator at the research centre will be sent to the PI/CoI/coordinators. This must be sent to CCRH headquarters/ CRI, Noida (DP coordinating centre) within 7 working days of completion of PME. The participants found fit will be enrolled as Provers and a unique identity code (UIC), based on next available number on the randomization list, will be generated for each prover.

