9.4.7 Coding/randomization

The UIC of the prover will be used for randomization for:

- Inter- individual control: 30% of the provers will be randomized into placebo group
- Intra-individual control: The drug-placebo sequence will be randomized for each prover in the verum group.

Intra-individual control is proposed to be maintained during the proving process to prevent incorrect attribution of symptoms to the IPS^[7].

The randomization will be done using computerized random number charts for allocation to intervention. This list will be used as the basis for the preparation and labeling of the study medication. Intervention allocation will be concealed until the proving is completed and the database has been locked. The sealed randomization list will be stored by the principal investigator and co-investigator at CCRH headquarters.

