9.4.10 Study Medication

Drugs in compliance with pharmacopoeial standards from GMP compliant manufacturers would only be procured. The alcohol to be used as placebo will also be purchased from GMP compliant pharmaceutical firm approved by the Council. The IPS will be prepared in the form of globules of size 30 and will be packed in the form of 1 dram glass bottles, labeled with serial number, prover's code and date of packaging. The placebo will be prepared similarly (dispensing alcohol impregnated globules of size 30) and labeled with serial number, prover's code and date of packaging.

The study medication will be labeled with the following information:

- Study medication protocol-code
- Sponsor: CCRH, India
- Dosage: 4 times xxx a day
- Batches XXX/XXX (batches for both IPS/Placebo production)
- Date:
- Date expiry:
- Subject/randomization No.:

Labeling will take place separately for IPS and placebo. The IPS and placebo medication will be packed in two separate lots/bundles.

The preparation of the IPS/placebo as study medication, for dispensing to individual provers will be done separately to avoid mixing of drugs and placebo batches. This would be done at the pharmacy at CCRH headquarters/CRI, Noida under direct supervision of the PI/coordinator.

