11. STUDY DURATION

The duration of proving for each prover will depend upon the symptoms produced and the subsequent wash out periods, needed, before subsequent doses can be given.

Expected duration for study

11.1 At research centre level:

- Prover screening: 1 week
- PME: 2 weeks (for completion of PME at a centre)
- Run in period (till receipt of IP batches): 2 weeks (to a maximum of 4 weeks)
- Administration of first batch: 3 days
- First washout period: 30 days (+ days for which symptoms persisted)
- Administration of second batch: 3 days
- Second washout period: 30 days (+ days for which symptoms persisted)
- Administration of third batch: 3 days
- Third washout period: 30 days (+ days for which symptoms persisted)
- TME: 1 week (to 2 weeks for completion of PME at a centre)

[figure not shown]
In case where no symptoms appear, a symptom free period of 30 days is maintained. In case(s) where symptoms appear, the observation period for each prover will vary depending on the duration for which the proving symptoms persist, subsequently followed by a 30 day symptom free washout period. (See section 9.4.17 for details)

As such for proving of each IPS an approximate duration of 7 months to 12 months is needed.

11.2 At Headquarters level, the study duration will include:

- Protocol preparation, regulatory approval, pretrial preparations: 2 months
- PME Assessment, randomization and allotment of batches, preparation of batches: 2 weeks (to a maximum of 3 weeks)
- Monitoring and supervision of study at research centre level: 7 months (to approx. 12 months)
- Data compilation & de-coding & analysis: 2 months
- Report preparation: 1 month

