16.2 At Headquarters

The study PI will review the original source documents & the data received from the investigators. The PI/Co-I will inform the investigators about the discrepancies in the records. All study related data, reports, meeting minutes, review and assessment records, monitoring records and documents would be kept at one place in the custody of Co-I. The proving data will be entered in the computer and maintained in MS excel formats.

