Based upon the findings of examination of eye, whether the volunteer is suitable or not for enrollment in proving (chose the relevant option)	Suitable for proving Not suitable for proving
Name of the consultant	
Date of examination	
Signature of the consultant	
Stamp	

To be filled by ENT consultant

ENT

1. Is there any abnormality in the form or function any disorder of the Ear?

No

Yes

Abnormal findings	Associated symptoms, if any	When possibly did it start?	Possible illness, disability or condition	Further tests required/ recommended

2. Is there any defect in hearing or speech?

No

Yes

Abnormal findings	Associated symptoms, if any	When possibly did it start?	Possible illness, disability or condition	Further tests required/ recommended

3. Please detail the findings of:

a. Auriscopic examination

b. Hearing tests

c. Tuning fork test

4. Is there any abnormality in the form or function any disorder of the Nose ?

No

Yes

Abnormal findings	Associated symptoms, if any	When possibly did it start?	Possible illness, disability or condition	Further tests required/ recommended

5. Is there any abnormality in the form or function any disorder of the Throat?

No

Yes

Abnormal findings	Associated symptoms, if any	When possibly did it start?	Possible illness, disability or condition	Further tests required/ recommended

Observations- any of the factors which make the participant unfit for proving as per protocol	1
	2
	3
	4
	5
Based upon the findings of ENT examination, whether the volunteer is suitable or not for enrollment in proving (chosed the relevant option)	Suitable for proving Not suitable for proving
Name of the consultant	
Date of examination	
Signature of the consultant	
Stamp	

CASE SUMMARY

To be filled by site investigator after completion of Form D, Part-II by the respective consultants

Constitution of prover

Specific observations

Clinical abnormality, if any

Pathological abnormality, if any

Radiological abnormality, if any

Participant recommended for proving: Yes

No

Signature of Site investigator

Name: _____

Date: _____

Stamp: _____

Form E Part 2

DRUG INTAKE PERIOD

Name of the Prover.....Proving Code No. CCRH/.....Batch No.....

Day	Dose	Date	Time of intake of the drug	Symptoms(s)/ any change in bodily functions/change in mental state in order of their appearance*	Time of		Intensity of symptoms	Any change(s) in lifestyle, circumstances, environment, etc.
					Appearance	Disappearance		
Day 1	1							

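### Headquarters roles that assess volunteers, oversee preparation of the medication and query records also hold the randomisation list, so the promised concealment until database lock is not secured against them

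*Protocol*

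**What the plan says.** **Entry.** Section 9.4.5 states: "The PME of the participants found fit as identified by the site investigator at the research centre will be sent to the PI/CoI/coordinators". Those found fit are enrolled and given a code taken from the next free place on the list: "The participants found fit will be enrolled as Provers and a unique identity code (UIC), based on next available number on the randomization list". Section 11.2 lists the headquarters task as one step: "PME Assessment, randomization and allotment of batches, preparation of batches: 2 weeks" (three weeks at most). On the Form D case summary the site investigator completes the line "Participant recommended for proving: Yes" or no.

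**The list.** Section 9.4.7 states: "The sealed randomization list will be stored by the principal investigator and co-investigator at CCRH headquarters". It also states: "This list will be used as the basis for the preparation and labeling of the study medication". The same section promises that allocation stays concealed until the proving is finished and the database is locked. Section 9.4.10 has each prover's medication prepared at the headquarters/CRI Noida pharmacy "under direct supervision of the PI/coordinator", with active and placebo material packed in separate lots.

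**Blinding and data review.** Section 9.4.8 names site investigators and participants as blind to allocation and does not name headquarters staff. Section 16.2 states: "The study PI will review the original source documents & the data received from the investigators", and has the PI/Co-I raise discrepancies with the sites. Section 13.3 has the coordinator build the database and the PI break the codes. Sections 15.3 and 15.4 have the PI un-blind when an adverse event is reported.

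**The concern.** Concealment keeps the next allocation from influencing who is accepted, or in what order accepted volunteers take their numbers. It works only if the people who can influence those steps cannot consult the list. Here they are the same roles, and no independent holder of the list is named.

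The same roles then check narrative symptom records during the trial. Under section 13.4 a symptom is dropped from the drug picture only if it is identical under drug and placebo in location, sensation, modalities and concomitants. One clarified detail can therefore decide whether a symptom counts as drug-related, and a query raised with knowledge of the arm can matter. The segregation of drug from placebo symptoms is the trial's control for attribution. Analysis cannot restore comparability lost at entry.

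**Working it through.** The point concerns separation of roles, so the check is to trace each function through the protocol.

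| Function | Section | PI | Co-I | Coordinator |
|---|---|---|---|---|
| Receives PMEs for enrolment | 9.4.5 | yes | yes | yes |
| Stores the randomisation list | 9.4.7 | yes | yes | not named |
| Supervises preparation | 9.4.10 | yes, or coordinator | not named | yes, or PI |
| Reviews source documents | 16.2 | yes | not named | not named |
| Raises discrepancies with sites | 16.2 | yes, or Co-I | yes, or PI | not named |
| Builds the database | 13.3 | not named | not named | yes |
| Breaks the codes | 13.3, 15.4 | yes | not named | not named |
| Named as blind to allocation | 9.4.8 | no | no | no |

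The PI can hold every function except building the database. The Co-I shares receipt of PMEs, custody of the list and queries. The coordinator can combine receipt of PMEs, supervision of preparation and database building.

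**Does the list exist before acceptance?** Section 9.4.5 speaks of the next available number, so the list pre-exists and each enrolment uses its next entry.

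**Can it stay sealed until lock?** Section 11.2 places allotment and preparation of batches at headquarters after PME assessment, before the first batch is dosed. The research-centre phase then runs about 7 to 12 months. The list is the basis for labelling, so someone must use it well before lock. The only supervision named is by the PI/coordinator.

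**Is order of entry fixed?** Each centre enrols 15 to 25 volunteers and the minimum total is 40 (section 9.3). Since 40/25 = 1.6, at least two centres are needed. PMEs reach headquarters within 7 working days of completion. No rule says in what order those accepted take numbers.

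**Does data review happen before lock?** Section 13 has sites send updates after the PME, after each batch with its observation and washout, and after the terminal examination. Section 16.1 sends originals to headquarters at the end of each phase. Section 16.2 review can therefore take place during the trial.

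**How many enrolments are exposed?** All of them: at 70/30 (section 8), 40 × 0.70 = 28 verum and 40 × 0.30 = 12 placebo.

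**The case against.** *Fitness is judged mainly at the site.* Section 9.4.5 forwards PMEs of people the site has already found fit. Sections 9.4.4 and 24.1 rely on experts, and each consultant marks suitability on Form D. A reader might infer that headquarters makes the final enrolment decision, but 9.4.5 does not say so. That reading rests on the undefined PME assessment in 11.2 and on the Form D line being a recommendation. The objection stands as far as it goes. Even if sites decide fitness alone, headquarters still assigns the numbers and queries the records.

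*The list is sealed.* A reader might infer that the assessors see the next arm when they accept a volunteer. The documents show custody and necessary use, not viewing. A sealed master with a separate pharmacy copy is not excluded. Section 9.4.7 also says the code is used for randomisation, and 11.2 lists assessment before randomisation, both compatible with acceptance being settled first. The sequence is therefore ambiguous, and no text secures it.

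*Biased querying is speculative.* Section 16.2 mentions only discrepancies. Blinded site investigators elicit and classify symptoms, and 13.3 puts symptom entry before de-coding. It would be wrong to infer that queries differ by arm; the text shows only that nothing prevents it.

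*No effect can be quantified.* A reader might want a percentage-point shift between arms. The protocol supports none: both incidence measures in 14.2 are defined only for volunteers taking the active substance, and placebo data enter by removing identical symptoms (13.4). The verum group's own placebo batch (9.4.9) is a within-person control that selective entry would not remove.

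**Conclusion.** The point holds as a weakness in role separation. The concealment stated in 9.4.7 is not secured against headquarters roles that receive and assess PMEs, hold the list, supervise preparation from it and query symptom records. Its scope is every enrolment, at least 40 provers. The size of any bias is unknown, and the documents give no evidence that selection or unequal querying occurs.

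The conclusion rests on two readings. The first is that the list described in 9.4.7 is the one used for labelling, which the text supports directly. The second is that PME assessment in 11.2 involves some judgement, which is an inference. If the second fails, exposure through order of entry and through queries remains. Because the remedy is cheap, it is worth making before enrolment starts.

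**What to change.** (a) **Section 9.4.5.** Require a dated, ordered register of accepted provers for each centre, signed before any identity code is assigned. Codes are then assigned strictly in that order.

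(b) **Sections 9.4.7 and 9.4.10.** Have the list held and used only by existing pharmacy staff at headquarters/CRI Noida who take no part in PME assessment, data queries or database building. Replace PI/coordinator supervision of preparation accordingly. If 9.4.10 is left as it is, an assessor could still learn allocations while supervising.

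(c) **Section 9.4.8.** State that the PI, Co-I and coordinators who assess PMEs, query records or build the database are blind to allocation until database lock. Reconcile this with the adverse-event un-blinding in 15.3 and 15.4 by routing each code break through the pharmacy and logging it. Section 15.4 already asks for a record of who saw what, when and why. Nothing here changes when a code may be broken.

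The cost is protocol wording and a reassignment of custody among existing staff. The downside is small: a code break needs a request to the pharmacy.
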